5 SYNOPSIS AND SCHEDULE OF EVENTS

5.1 Synopsis

Title of Study Protocol: A Phase 1/2a Study of Cryopreserved Ex Vivo Expanded Polyclonal CD4 ⁺ CD127 ^{lo/-} CD25 ⁺ T Regulatory Cells (cePolyTregs) for the Treatment of Acute Respiratory Distress Syndrome (ARDS) Associated with SARS-CoV-2 Infection (regARDS)
Protocol Number: UCSF-cePolyTregs-01
Name of Sponsor Company: University of California, San Francisco [name]
Name of Finished Product: cePolyTregs
Phase of Development: Phase 1/2a
Investigators/Study Centers: Up to 12 centers
Objectives: Primary Objectives Parts 1 and 2: To evaluate the safety and tolerability of cePolyTregs administered as a single intravenous (IV) dose in subjects with ARDS associated with SARS-CoV-2 infection Part 2 (Phase 2a): To evaluate the efficacy of cePolyTregs administered as a single IV dose in subjects with ARDS associated with SARS-CoV-2 infection Secondary Objectives Part 1 (Phase 1): To determine the Recommended Phase 2 Dose (RP2D) of cePolyTregs administered as a single IV dose in subjects with ARDS associated with SARS-CoV-2 infection Parts 1 and 2: To determine the pharmacodynamics and biomarker changes associated with cePolyTregs administration as a single IV dose in subjects with ARDS associated with SARS-CoV-2 infection Exploratory Objective To determine the clinical activity of a single IV dose of cePolyTregs on extrapulmonary manifestations of infection with SARS-CoV-2
Endpoints: Primary Endpoints Part 1 (Phase 1): Safety and tolerability of cePolyTregs as assessed by dose limiting toxicities (DLTs), defined as any related treatment-emergent adverse event (TEAE) with an NCI CTCAE 5.0 grade ≥ 3 which also represents a shift from baseline clinical status of ≥ 1 NCI CTCAE grade. Part 2 (Phase 2a): Efficacy of cePolyTregs compared with placebo/SOC, as assessed by time to recovery, defined as the first day during the 28 days after randomization on which a subject meets the criteria for category 0, 1, 2, 3, or 4 on the WHO severity scale for COVID-19 pulmonary syndrome. Safety of cePolyTregs as assessed by the occurrence of related TEAEs with an NCI CTCAE 5.0 grade ≥ 3 .

Secondary Safety EndpointsPart 1 (Phase 1):

RP2D of cePolyTregs as assessed by cumulative safety, tolerability, pharmacodynamic and biomarker changes associated with administration of cePolyTregs compared with placebo/SOC

Parts 1 and 2:

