11.14 Assessment of Concomitant Medications

Reportable concomitant medications will be captured in the electronic database system as defined below based on timing of study drug administration. Medication doses can be reported as ranges and changes in dose can be reported if deemed clinically significant by the investigator.

Prior to study drug administration:

- Vaccine status
- COVID-specific therapies
- Immunosuppressive therapies (steroids, DMARDs, biologics)
- Antibiotics
- Vasopressors

Following study drug administration:

- COVID-specific therapies
- Immunosuppressive therapies
- Antibiotics
- Vasopressors
- Neuromuscular blockade
- Any treatment for an AE
- Changes in BP meds or addition of new meds (hypotension + hypoxemia)
- Change in oxygen/ventilator

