12 ADVERSE EVENTS

An AE is defined as any unfavorable and unintended sign (including an abnormal laboratory finding), symptom, or disease or any worsening of a pre-existing condition temporally associated with the use of a study drug, whether or not related to study drug. From signing the ICF to study drug administration, all SAEs and nonserious AEs related to protocol-mandated procedures will be recorded on the SAE/AE eCRF. All other untoward medical occurrences observed during screening, including exacerbation or changes in the medical and surgical history will be captured on the medical and surgical history eCRF.

An AE that occurs before the first administration of the study drug will be considered a pre-treatment AE. A TEAE is defined as any adverse event that was not present before the first administration of the study drug, or any event already present, that worsens in either severity or frequency, following exposure to the study drug. AEs that occur after treatment with IP or during the Safety Follow-up Period will be documented on the AE eCRF. The investigator will assess AE severity, the causality relationship of the AE to study drug, and will treat the subject as medically required to ensure the subject's safety.

AEs will be captured through the EOS Visit at Day 56 or the ET Visit. Reportable adverse events are defined based on timing of study drug administration, as follows:

- Treatment – Day 7: AEs grade 3+ that are not expected to occur in critically ill patients, per the discretion of the investigator.
- Treatment Day 8 – Day84/EOT: AEs grade 4+ that are not expected to occur in critically ill patients, per the discretion of the investigator.

Events expected in the critically ill and are being captured in the eCRF should not be reported as adverse events unless considered to be related to the study drug or unexpectedly severe or frequent per the discretion of the investigator. These include but are not limited to; need for vasoactive drugs or fluids for hypotension, decreased PaO₂/FiO₂, transient hypoxemia, need for renal replacement therapy, or worsening acute respiratory distress syndrome.

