12.5 Causality Assessment

The investigator or qualified sub-investigator is responsible for assessing and assigning the causality relationship of the event to study drug or study-related procedures (e.g., invasive

UCSF	Clinical Study Protocol No. UCSF-cePolyTregs-01	Page 54 of 72
------	---	---------------

procedures, such as venipuncture) using clinical judgment and the following categories of relatedness:

- Related: There is at least some possibility that the AE could be related to study medication administration.
- Not related: There is a high degree of certainty that the AE is NOT related to study medication administration.

In making a causality assessment of an AE, it should be considered as to whether or not the AE is expected to occur due to the underlying disease, based on the investigator's clinical experience.

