13.6 Safety Analyses

All safety data summaries will use the safety population.

The number and percent of subjects experiencing any DLTs will be presented by cohort. A listing of DLTs will also be provided.

Adverse events (including DLTs) will be coded using MedDRA (v 20.1, or the current version) and will be graded by the investigator using the NCI CTCAE v 5.0 or the current version. Subject incidence of TEAEs, TESAEs, TEAEs leading to treatment discontinuation, AESIs, and TEAEs with an outcome of death will be summarized by SOC and preferred term. Adverse events will also be further summarized by worst CTCAE severity grade and relationship to study drug. In addition, AESIs as described in Section [Error! Reference source not found.](#) will also be summarized by SOC, preferred term, and worst severity grade.

Clinical laboratory data will be summarized descriptively, and the summaries will include observed values at collection time points and their changes from baseline. All laboratory parameters that can be graded using the CTCAE v 5.0 will be graded. For selected parameters, the following summaries may be produced:

- Worst postbaseline severity grade
- Shift summary of baseline grade to worst postbaseline severity grade.

Safety evaluations may also include changes in the subject's vital signs and ECG findings.

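### Expected organ-failure events are kept out of adverse event reporting at the blinded investigator's discretion, and Section 13.6 specifies no by-arm summary of the captured data, so an excess on cePolyTregs could be missed or understated in the AE tables

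*Combined protocol and SAP*

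**What the plan says.** Section 12 (Adverse Events) sets two filters on what becomes an AE.

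- **General threshold.** From treatment to Day 7, grade 3 or higher events are reportable if not expected in critical illness. From Day 8 the rule narrows to "AEs grade 4+ that are not expected to occur in critically ill patients, per the discretion of the investigator".
- **Exemption.** "Events expected in the critically ill and are being captured in the eCRF should not be reported as adverse events". The examples cover vasoactive drugs or fluids for low blood pressure, falling PaO2/FiO2, brief hypoxemia, and "need for renal replacement therapy, or worsening acute respiratory distress syndrome". The exemption applies "unless considered to be related to the study drug or unexpectedly severe or frequent per the discretion of the investigator".

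Section 12.5 sets a low bar for a related event: "There is at least some possibility that the AE could be related to study medication administration". It also tells the investigator to consider whether the underlying disease would be expected to produce the event. Section 12.6.2 requires every SAE to be reported whatever its cause. Section 10.7 keeps investigators blinded throughout Part 2.

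On analysis, Section 13.6 states: "Subject incidence of TEAEs, TESAEs, TEAEs leading to treatment discontinuation, AESIs, and TEAEs with an outcome of death will be summarized". It adds DLTs and laboratory summaries, with vital signs and ECGs as optional. Section 13.1 makes the Part 2 safety analysis descriptive, without formal comparison of arms.

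**The concern.** Exempting expected events from one-by-one reporting is sensible in an intensive care trial, provided that the same events are then counted and set side by side by arm. For a common background event, causality usually cannot be settled in the individual patient. Harm shows only as a difference in frequency between randomized groups.

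The plan takes the first step and does not specify the second. It exempts the events because they are captured elsewhere, but Section 13.6 contains no table that draws on that capture. What reaches the AE tables depends on investigators who do not know the arm and who each see a small part of the trial.

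Safety is a primary objective of Part 2 (Section 8.5.1), and Section 8.2 says cePolyTregs has not been studied clinically before. More organ support on the active arm is something that the safety report should be able to show.

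**Working it through.** **1. The plan's own safety figure.** Section 13.2 gives a 95% interval of (0.179, 0.446) for 15 SAEs among 50 subjects. The exact Clopper-Pearson interval has lower limit Beta(0.025; 15, 36) = 0.1786 and upper limit Beta(0.975; 16, 35) = 0.4461. The figure reproduces. It describes one arm's SAE rate and says nothing about the exempted events.

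**2. What one site can see.** The synopsis allows "Up to 12 centers", and Part 2 randomizes 100 subjects 1:1. That averages 100/12 = 8.3 subjects per site, or about 4 per arm. This is the smallest possible average; fewer active centers would mean more subjects each.

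The documents give no rates of RRT or vasopressor use, so the rates below are assumptions. Take 20% on placebo and 40% on cePolyTregs, which pool to 30%. A blinded investigator with 8 subjects expects 8 × 0.30 = 2.4 events, against 8 × 0.20 = 1.6 with no harm. Taking 4 or more events as an illustrative alarm level:

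- with the excess, P(X ≥ 4), X ~ Binomial(8, 0.30), is 0.194;
- without it, P(X ≥ 4), X ~ Binomial(8, 0.20), is 0.056.

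So a doubled rate would pass without alarm at about four sites in five.

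**3. What a by-arm table can see.** Power of the pooled two-proportion z test by exact enumeration, 50 per arm, two-sided 10%:

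| Assumed placebo vs cePolyTregs | Expected subjects | Power |
|---|---|---|
| 20% vs 40% | 10 vs 20 | 0.72 |
| 30% vs 50% | 15 vs 25 | 0.66 |
| 10% vs 20% | 5 vs 10 | 0.40 |
| 20% vs 30% | 10 vs 15 | 0.32 |

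For 20% vs 40%, the 90% interval for the risk difference has half-width 1.645 × √(0.20 × 0.80/50 + 0.40 × 0.60/50) = 1.645 × 0.0894 = 0.147, so roughly 5 to 35 percentage points. These figures treat all 50 subjects per arm as at risk. Subjects already on vasopressors or in WHO category 7 at baseline are not at risk of a new event, so precision for those rows would be lower.

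**4. What the AE table would show.** If investigators reported a fraction q of these events, the expected counts in the 20% vs 40% case are 50 × 0.20 × q and 50 × 0.40 × q. For q = 0.10 that is 1 vs 2 subjects; for q = 0.25 it is 2.5 vs 5. The fraction is an assumption.

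**5. Planned analyses that overlap with the exempted events.**

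- *WHO scale (8.6.3, 11.6).* The planned endpoints count recovery or improvement, so a move from category 6 to 7 is not tabulated. Category 7 also pools pressors, RRT and ECMO.
- *SOFA (8.6.3, 11.7).* It includes vasoactive drugs, creatinine or urine output, and PaO2/FiO2, but has no RRT item. It is scored daily in hospital (5.2, footnotes a and f) but summarized as mean and median on four days, so support begun and ended between those days is lost.
- *Ventilation and mortality (8.6.3).* Compared by arm, but neither counts RRT or vasopressor use.
- *Creatinine (11.10, 13.6).* Summarized, but RRT itself lowers it.
- *Hypoxemia AESI (12.2).* Limited to the first 6 hours after exposure.

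**The case against.** The case against is substantial, and much of it stands.

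- **Three triggers, not one.** A reader might infer that only an unexpectedly high frequency lifts the exemption. Relatedness and unexpected severity also lift it, and the relatedness bar is low. The Part 2 primary safety endpoint counts related events of grade 3 or higher (8.6.1), and Section 12 expressly keeps related events outside the exemption. Two limits remain: Section 12.5 also points the investigator to the underlying disease, and the severity trigger does not detect an excess of events of ordinary severity.
- **SAEs.** Section 12.6.2 has no stated exception for expected events, and treatment-emergent SAEs are tabulated. But Section 12.1 defines an SAE as a kind of AE, and Section 12 says these events are not reported as AEs. Sites could read this either way.
- **Other by-arm results.** SOFA, ventilation and mortality are compared between arms, and an unblinded DSMB reviews all available clinical and laboratory data (8.1.5, 8.2). An excess could surface there, though no organ-support table is specified for either purpose.
- **RRT capture.** A reader might infer that RRT is not recorded because Section 11.14 omits it. That section begins "Reportable concomitant medications will be captured in the electronic database system as defined below" and is a medication list, so the absence of a procedure proves little. Section 12 presupposes capture, and the eCRF is not among the documents.
- **Deferred detail.** Section 13 leaves detailed methods to a separate SAP and Section 8.8.1 leaves DSMB detail to a charter. The missing table is shown only for the protocol's own statistical section.

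**Conclusion.** The point holds as a gap in the planned safety analysis. An excess of RRT, vasopressor use or worsening oxygenation on cePolyTregs could be missed or understated in the AE tables, because reporting rests on case-by-case judgement by blinded investigators and no by-arm safety summary of the captured data is specified. The stronger reading, that such an excess would be absent from the safety results altogether, is not supported: the related, severe and SAE routes stay open, and several overlapping outcomes are compared by arm.

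The size depends on assumed rates. A by-arm table would be informative for a large difference (power about 0.72 for 20% vs 40%, 0.66 for 30% vs 50%) and weak for smaller ones (0.40 for 10% vs 20%, 0.32 for 20% vs 30%). It would be a description with intervals and could not serve as a definitive test. The change should be made; it does not call the design into question.

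**What to change.** 1. Add to Section 13.6 a descriptive by-arm table through Day 28 of first post-infusion RRT, new vasopressor use, progression to WHO category 7 and worsening PaO2/FiO2, with risk differences and 90% confidence intervals. This fits the statement in Section 13.1 that arms are not formally compared.
2. Define each row before unblinding: who is at risk at baseline, how deaths are counted, and what is used when no arterial gas is available, since Section 11.8 collects PaO2 only if one was drawn in the morning window.
3. Build the table from the daily in-hospital WHO and SOFA scores, ventilator data and vasopressor records already collected, and give it to the unblinded DSMB.
4. Keep all three investigator triggers in Section 12. The table adds a route and should not replace one.
5. Confirm that RRT start is captured in the eCRF, and add it if it is not.
6. Reconcile the Section 12 exemption with the all-SAE rule in Section 12.6.2, so that sites know how to handle an expected event that meets a seriousness criterion.

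The cost is a little programming, one more descriptive comparison to interpret and, if RRT start is not yet recorded, a small eCRF addition.

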12.1 Serious Adverse Events

A *serious adverse event* (SAE) is defined as any AE occurring at any dose that results in any of the following outcomes:

- Death
- Life-threatening AE (Note: A life-threatening AE is one that, in the view of the investigator places the subject at immediate risk of death from the reaction as it occurred)
- Hospitalization or prolongation of existing hospitalization
- A persistent or significant disability/incapacity
- A congenital anomaly/birth defect.

Important medical events that may not result in death, be life threatening, or require hospitalization may be considered an SAE when, based upon appropriate medical judgment, they may jeopardize the subject and may require medical or surgical intervention to prevent one of the outcomes listed in this definition. Examples of such medical events include blood dyscrasias or convulsions that do not result in subject hospitalization, or the development of drug dependency or drug abuse.

12.2 Adverse Events of Special Interest

To date, there have been no clinical studies using cePolyTregs, and nonclinical studies with autologous, homologous products have not demonstrated specific toxicities related to administration of adoptively transferred Tregs. Potential adverse events of interest in the COVID-19 setting based on the biology of cePolyTregs include infusion/hypersensitivity reactions and infections including pneumonia and those involving pathogens not anticipated in a COVID-19 setting; these clinical parameters will be closely monitored in the current study.

The following events are defined as AESIs that should be reported by completing the Adverse Event eCRF and AESI eCRFs within 24 hours of the site's awareness of them, even if they do not meet criteria for an SAE:

- Evidence of hypersensitivity or transfusion incompatibility (e.g. new rash, urticaria, new onset bronchospasm).
- Diagnostically or clinically confirmed respiratory infections that were not present before study drug infusion AND that require a treatment course with antimicrobial agents, operative management, or procedural drainage.
- Within 6 hours of IP exposure:
 - New ventricular tachycardia, ventricular fibrillation, or asystole or any cardiac arrhythmia requiring cardioversion.
 - Hypoxemia requiring an increase in FiO₂ of 0.2 or more and/or an increase in PEEP of 5 cm H₂O or more to maintain SpO₂ in the target range of 88–95%, for a sustained duration (>2 hours) and not associated with a care procedure.

- Pulmonary Embolism

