7.2.1 Mechanism of Action

Tregs are a subset of CD4⁺ T cells that function to maintain immune system homeostasis and preserve tolerance to self-antigens. The function of Tregs in maintaining immune tolerance can be harnessed through Treg cell therapy for treating various immunological diseases ([Tang 2006](#)). Tregs have a unique and robust therapeutic profile that is distinct from small-molecule and biologic immunosuppressants and anti-inflammatory drugs. Tregs have the ability to migrate to

sites of inflammation and have over 30 different immune regulatory mechanisms to respond to different inflammatory conditions (Tang 2008). While requiring specific T cell receptor-mediated activation to express regulatory activity, Treg effector function appears to work by bystander suppression, regulating local inflammatory responses through a combination of cell-cell contact and suppressive cytokine production. Tregs are long-lived in autologous recipients, and tolerance conferred by autologous Treg therapy can persist even when the therapeutic cells no longer persist (Kendal 2011; Waldmann 2008). In contrast, allogeneic Tregs such as cePolyTregs are eliminated by the recipient host immune system within weeks, with their therapeutic effects having already been manifested as suggested by previous experience in acute and chronic graft-versus-host disease (GVHD; Blazar 2018, Brunstein 2010, Pierini 2015).

Adoptive Tregs therapies have been shown to be effective in dozens of animal models of autoimmunity, organ transplantation, allergy and asthma, and degenerative diseases such as brain dementias, muscular dystrophy and cardiac disease.

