8.4.1 Dosing Estimate Based on Rodent Models

The effective dose of cePolyTregs for controlling inflammation in ARDS in humans is currently unknown but there are indications from rodent studies. In a mouse model of LPS-induced and viral infection-induced ARDS, a single infusion of 1 million syngeneic Tregs was effective in disease prevention (D'Alessio 2009). Using the traditional exponential allometry for molecular therapy, 1 million cells per dose in a 20 g mouse would translate into ~400 million cells in a 70 kg human with an exponent of 0.75.

There are a number of limitations to this estimate. 1) No dose titration experiments in mice were reported so the minimal effective dose or optimal dose may be different from the estimated 1 million cells. 2) There is no established method for allometric scaling of cellular therapies that have distinct PK and PD from molecular therapies. 3) Mouse models of ARDS used syngeneic (i.e. autologous) Tregs. Allogeneic cePolyTregs proposed for this study contain 10% to 20% of cells that are reactive to mis-matched HLA combined with the existing self-antigen recognition repertoire. These cells are expected to be activated after infusion and proliferate in the recipient, which may potentiate the impact of the infused dose. 4) The Tregs used in studies of mouse models used mouse Tregs whereas the cePolyTregs proposed for use in this study are human Tregs. Due to interspecies incompatibilities of intercellular communications, testing human Treg products limits the utility of mouse models.

Thus, the actual effective dose of cePolyTregs in humans cannot be accurately estimated based on available animal data. The ~400 million cells per dose estimate can be viewed as a reference at best and thus is proposed as the top dose being explored in the current study.

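### Graft-versus-host disease is not named as an adverse event of special interest, and non-serious gut or liver events up to grade 3 after Day 7 are generally not reportable, so a report of none would be weak evidence of absence

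*Combined protocol and SAP*

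**What the plan says.** Section 12.2 sets out the risks expected from the product: "Potential adverse events of interest in the COVID-19 setting based on the biology of cePolyTregs include infusion/hypersensitivity reactions and infections including pneumonia". Its reportable list covers hypersensitivity or transfusion incompatibility, treated respiratory infection, arrhythmia and hypoxemia within 6 hours of exposure, and pulmonary embolism. The item closest to an alloreactive sign is the first: "Evidence of hypersensitivity or transfusion incompatibility (e.g. new rash, urticaria, new onset bronchospasm". It carries no grade or day limit.

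The product comes from unrelated donors (Synopsis, Investigational Products). Section 8.4.1 states: "Allogeneic cePolyTregs proposed for this study contain 10% to 20% of cells that are reactive to mis-matched HLA", and continues: "These cells are expected to be activated after infusion and proliferate in the recipient, which may potentiate the impact of the infused dose". On persistence, Section 7.2.1 says "allogeneic Tregs such as cePolyTregs are eliminated by the recipient host immune system within weeks"; Section 8.1.1 expects exposure of about 2 weeks.

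Section 12 limits what must be reported as an adverse event. Up to Day 7: "Treatment – Day 7: AEs grade 3+ that are not expected to occur in critically ill patients". From Day 8 to Day 84: "AEs grade 4+ that are not expected to occur in critically ill patients". Both limits are at the investigator's discretion.

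**The concern.** Section 12.2 says it draws its list from the product's biology, but it does not take up the one biological property that 8.4.1 singles out, even to dismiss it. An alloreactive reaction could develop while the cells persist, which the protocol puts at weeks. The dose-limiting toxicity window closes at 7 days, and the reporting threshold rises to grade 4 on Day 8.

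Sections 8.2 and 12.2 say that there have been no clinical studies of cePolyTregs, and safety is a primary objective of both parts. Much of the supporting safety evidence cannot speak to a donor-against-host reaction: the mouse studies in 7.3.3 used syngeneic cells, and the PolyTregs experience in 8.4.3 is autologous. A reader of the final report would want to know whether such a reaction was seen, and the plan has no category that answers this.

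**Working it through.** The plan gives no GVHD rate and no capture rate, so there is no stated figure to reproduce. The check is mainly a tracing of the text.

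**1. Where GVHD is named.** In the text available it appears as an abbreviation (Section 6), in background and nonclinical text (7.2.1, 7.3.1, 7.3.3), as a description of earlier studies (8.2) and in reference titles. It does not appear among the anticipated risks in 8.2, 8.2.1 and 8.2.2, in the AESI endpoint (Synopsis, 8.6.2) or in the AESI list (12.2). No definition, grading or dedicated assessment is given.

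**2. Where each sign would go.** I assume that skin, liver and gut are the organs in which such a reaction would show; the protocol is silent on this.

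| Finding after Day 7 | Channel | Would it be identified? |
|---|---|---|
| New rash, any grade | AESI, 24 hours (12.2) | Captured, labelled hypersensitivity or transfusion incompatibility |
| Any event meeting an SAE criterion | SAE report regardless of cause (12.6.2) | Captured, no GVHD category |
| Abnormal liver tests | Scheduled chemistry to Day 84 (5.2, 11.10); change and shift summaries (Synopsis, 13.6) | Values captured; nothing links them to skin or gut findings |
| Non-serious liver event recorded as an AE, grade 1 to 3 | Below the Section 12 threshold | Generally not reported as an AE |
| Non-serious gut event, grade 1 to 3 | Below the Section 12 threshold; no laboratory channel | Generally not reported |

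Up to Day 7 the same gap exists for grades 1 and 2. After screening, physical examinations are targeted to new complaints or changes from baseline (5.2, footnote e); no skin or gut review is required.

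**3. What zero reported cases would mean.** The inputs are up to 18 subjects in Part 1 and 50 of the 100 in Part 2: 18 + 50 = 68 treated at most, pooled over doses. With full capture, the one-sided 95% upper bound after zero cases is 1 − 0.05^(1/n):

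- n = 50: 1 − 0.05^(1/50) = 5.8%
- n = 68: 1 − 0.05^(1/68) = 4.3%

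If only a share s of cases is recorded, the bound on the true rate is that figure divided by s. The values of s below are assumptions chosen to show direction and are not estimates:

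| s (assumed) | n = 50 | n = 68 |
|---|---|---|
| 1 | 5.8% | 4.3% |
| 0.5 | 11.6% | 8.6% |
| 0.25 | 23.3% | 17.2% |

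**4. A contradiction found on the way.** Section 8.6.1 makes related TEAEs of grade 3 or higher a Part 2 primary safety endpoint, and 8.6.2 counts the type and frequency of TEAEs; neither has a Day 7 limit. Section 12 drops non-serious grade 3 events from Day 8. Section 12 also places the end-of-study visit at Day 56 in one sentence and runs reporting to Day 84 in another, while 8.1.5 puts that visit at Day 84.

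**The case against.** The strongest reply is that the hazard is not the protocol's. No section says cePolyTregs may cause GVHD. The product is a purified regulatory population, 8.4.1 presents proliferation as possibly strengthening the effect of the dose, 7.3.1 reports that Tregs improved GVHD score in mice, and 9.2 excludes known or suspected immunodeficiency and prior marrow or stem cell transplant. All of this stands. The point is an inference from 8.4.1, and it needs only a plausible mechanism. A reader might also infer that dexamethasone would prolong the cells' survival; nothing in the documents supports that.

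The second reply is that existing channels already look. A reader might infer that the trial could report no GVHD without having looked at all. The documents do not support that: new rash is an AESI at any grade and on any day, every SAE is reported, many grade 3 events would probably qualify as SAEs, and liver tests run to Day 84. Section 12.5 also sets a low bar for relatedness, and Section 12 lets events expected in critical illness be reported when judged related, although it is unclear whether the grade limits still apply. These channels narrow the gap but do not close it: non-serious gut events and clinical liver events up to grade 3 remain outside, and nothing prompts an investigator to connect the signs.

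Third, GVHD surveillance may be described elsewhere. The first part of Section 7.4, the Investigator's Brochure, the DSMB Charter and the separate analysis plan mentioned in Section 13 were not available, so this cannot be excluded. The reporting rule would still belong in 12.2.

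**Conclusion.** The point holds in a limited form. GVHD is not named as an AESI, although the protocol describes an allogeneic product with HLA-reactive cells expected to proliferate. Followed as written, the plan would generally not record non-serious gut or liver adverse events up to grade 3 after Day 7, and would file an alloreactive rash as hypersensitivity. A statement that no GVHD was reported would be weak evidence of absence.

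The only firm figure is the best case: zero cases among 68 fully observed subjects excludes rates above 4.3%. A reader might want to attach a specific capture percentage and a correspondingly higher bound. The documents supply no basis for one, so the other figures show direction only. The conclusion rests on reading 8.4.1 as a plausible mechanism for harm, which the protocol does not state.

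**What to change.** Add one item to the list in 12.2 and to the AESI endpoint in 8.6.2: *suspected or confirmed graft-versus-host disease (new skin, liver or gastrointestinal findings that the investigator considers possibly alloreactive and not explained by another cause), any grade, through Day 84*. State that it is exempt from the Section 12 grade thresholds. In 13.6, tabulate it separately from hypersensitivity.

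Reconcile Section 12 with 8.6.1 and 8.6.2, so that the grade 3 and higher related TEAEs and the overall TEAE counts named as endpoints are actually collected after Day 7. Correct the Day 56 and Day 84 conflict over the end-of-study visit.

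The cost is one list item, an eCRF option and a table row, with no new scheduled procedure. The real burden is more 24-hour AESI reports, each needing two forms, some of which will be drug rashes or liver-test changes judged unrelated. Requiring the investigator to consider the finding possibly alloreactive keeps that number down. Because examinations after screening are targeted, the new item will depend on staff being alert to these signs.
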